4.3 Intervention

Patients will receive sLe^a-KLH plus QS-21 subcutaneously during weeks 1,2,3,7 and 19. The first 3 patients will receive a 10 mcg dose of sLe^a and subsequently all patients will receive a 30 mcg dose of sLe^a. The dose of QS-21 is 100 mcg for the initial 13 patients. If immune responses are observed at the 100 mcg level of QS-21 then the dose of QS-21 will be escalated to 150 mcg, in a subsequent group of patients during weeks 1, 7 and 19. Blood samples will be obtained pre study and during weeks 1,2,3,5,7,9,13, 19 and 23 to assess for immune response.

sLe^a is one of multiple antigens found on breast cancer cells. Data from this trial will be used to determine whether the sLe^a antigen will be included in a future polyvalent construct. Ultimately we plan a multicenter randomized clinical trial to assess potential clinical benefit of immunization with a polyvalent construct in high risk breast cancer patients.

5.0 THERAPEUTIC/DIAGNOSTIC AGENTS

5.1 Clinical Material

5.1.1 Sialyl lewis^a (sLe^a)-KLH conjugate The conjugate is prepared at Optimus Pharmaceutical, Inc. sLe^a pentenyl glycoside was synthesized using a proprietary synthetic method by Optimus Pharmaceuticals, Inc. under GMP. Its identity was confirmed by MS and NMR. The glycoside was purified by reverse phase

chromatography and the purity established to be greater than 99% by NMR and HPLC analysis.

The pentenyl glycoside group on sLe^a was bound to M2C2H heterobifunctional linker following ozone treatment. Keyhole limpet hemocyanin (KLH) was activated by introduction of thiol groups on the KLH amino groups with 2-Iminothiolane. Activated KLH was mixed with sLe^a-M2C2H and the resulting sLe^a-M2C2H-KLH purified and washed by diafiltration. The carbohydrate and protein components were quantitated and the conjugate was tested for toxicity and immunogenicity in mice. The sLe^a/KLH ratio was determined to be greater than 600/1. The dose of sLe^a-KLH to be studied is 30 mcg. However, due to concerns regarding potential toxicity 3 patients will first be entered at a dose of 10mcg.

5.1.2 QS-21 QS-21 is a saponin prepared from the bark of Quillaja saponaria Molina. It will be supplied by Antigenics, Inc.. All injections will be vialed with a dose of 100 mcg of QS-21. If there is an immune response in at least six of the ten patients, then in the second group of patients, an additional 50 mcg of QS-21 will be added to the preparation during weeks 1, 7 and 19.

5.1.3 The injection will contain sLe^a-KLH conjugate 30 mcg (10 mcg for the first 3 patients) and QS-21 100 mcg per 1 ml 0.9% saline. It will be stored at -80°. The total volume per vial is 1.1 ml.

6.1 CRITERIA FOR SUBJECT ELIGIBILITY

Breast cancer patients with a history of metastatic disease will potentially be eligible.

6.2 Subject Inclusion Criteria

- **AJCC Stage IV breast cancer who have no evidence of disease**
OR
AJCC Stage IV breast cancer who have stable disease on hormonal therapy. Stable disease must be present for at least 2 months prior to enrollment in this study. Stable disease includes less than a 30% decrease or less than a 20% increase in the sum of the longest diameters of target lesions, taking as a reference the baseline sum of the longest diameters recorded at the last set of scans. Stable disease also includes no new target lesions and no unequivocal progression of non-target lesions.
(These patients may or may not have an elevation in the CA153 (BR2729) or CEA values).
- Performance status ≥ 80 (Karnofsky).
- Patients must have completed radiation, chemotherapy or surgery at least 4 weeks prior to treatment. Patients must have completed prior immunotherapy at least 6 weeks prior to vaccination. **Ongoing hormone therapy is permitted.**
- Pathology slides from the metastatic site must be reviewed by the Department of Pathology at MSKCC to confirm diagnosis.

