12.3 Clinical Response

Patients will be monitored for anti-tumor effect, although this is not a primary endpoint. Patients who have evidence of disease will be evaluated at week 19 or at the discretion of their physician. Responses will be categorized using RECIST response criteria as follows:

Complete Response (CR):

Target Response Criteria: The disappearance of all known disease and no new sites or disease related symptoms confirmed at least 4 weeks after initial documentation. All sites must be assessed, including non-measurable sites, such as effusions, or markers

Non-Target Response Criteria: Disappearance of all non-target lesions and normalization of tumor markers level confirmed at least 4 weeks after initial documentation.

Partial Response (PR):

Target Response Criteria: At least a 30% decrease in the sum of the longest diameters of target lesions, taking as a reference the baseline sum of the longest diameters confirmed at least 4 weeks after initial documentation. PR is also recorded when all measurable disease has completely disappeared, but a non-measurable component (i.e., ascites) is still present but not progressing.

Stable Disease (SD):

Target Response Criteria: Neither sufficient shrinkage to qualify for partial response nor sufficient increase to qualify for progressive disease.

Non-Target Response Criteria: Persistence of one or more non-target lesions and/or the maintenance of tumor marker level above the normal limits.

Progressive Disease (PD):

Target Response Criteria: At least a 20% increase in the sum of the longest diameters of target lesions, taking as reference the smallest sum of the longest diameters recorded since the treatment started; or the appearance of one or more new lesions; or the unequivocal progression of a non-target lesion.

Non-Target Response Criteria: Appearance of one or more non-target lesions and/or unequivocal progression of existing non-target lesions.

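### Section 6.2 bars only new target lesions at entry, while Section 12.3 counts any new lesion as progression; the entry rule's size limits and reference sum are also loosely worded

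*Combined protocol and SAP*

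**What the plan says.** Section 6.2 opens the trial to Stage IV patients with no evidence of disease, and to Stage IV patients whose disease is stable on hormonal therapy. Only the second group matters here. Its entry rule has four parts:

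- Duration: "Stable disease must be present for at least 2 months prior to enrollment in this study".
- Size: "Stable disease includes less than a 30% decrease or less than a 20% increase in the sum of the longest diameters of target lesions".
- Reference: "taking as a reference the baseline sum of the longest diameters recorded at the last set of scans".
- New lesions and non-target disease: "Stable disease also includes no new target lesions and no unequivocal progression of non-target lesions".

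Section 12.3 defines response and progression on study. For target lesions, progression is a rise of 20% or more in the summed diameters, with this reference and this alternative: "taking as reference the smallest sum of the longest diameters recorded since the treatment started; or the appearance of one or more new lesions". Clear worsening of a non-target lesion also counts. For non-target lesions it is "Appearance of one or more non-target lesions and/or unequivocal progression of existing non-target lesions". In the same section, stable target disease means that neither the shrinkage limit nor the growth limit has been reached.

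Section 2.1 says that clinical response is not an endpoint and will be reported descriptively. Section 14.0 treats circulating tumour cells (CTC) as exploratory.

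**The concern.** The protocol uses one term, stable disease, with two contents, and the entry version is the looser. A new lesion recorded as non-target counts as progression in Section 12.3 but is not named as a bar in Section 6.2. Two investigators could apply 6.2 to the same scans and reach different eligibility decisions, each with support in the text.

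What is at stake is the description of who was studied, and the results that depend on disease course:

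- Sections 1.0 and 6.2 describe the population as having no evidence of disease or stable disease. Section 3.3 reports similar immune responses in those two groups in earlier trials and gives no such support for progressing patients.
- Section 14.0 asks whether CTC decline in immune responders. Progression already under way at entry would blur that trend in a small sample.
- Three-monthly follow-up, including serology where feasible, runs until progression (Section 10.0, table footnote g; Section 12.1). An early progression shortens it.

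**Working it through.** The plan states no figure on this point, so there is none to reproduce. The check compares the clauses and adds simple arithmetic on the sum of longest diameters.

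**Step 1. New lesions.**

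| Finding | Section 6.2 (entry) | Section 12.3 (on study) |
|---|---|---|
| New target lesion | Barred | Progression |
| Clear worsening of an existing non-target lesion | Barred | Progression |
| New non-target lesion | Not named | Progression, under both the target and the non-target criteria |

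The third row is the inconsistency. Section 12.3 lists the appearance of a non-target lesion and the worsening of existing ones as two separate events. Section 6.2 names the second, and restricts its new-lesion clause to target lesions.

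**Step 2. The word *or*.** Let c be the percentage change in the sum. Read literally, 6.2 accepts c > −30 *or* c < +20, and every value of c meets at least one of these: c = +50 meets the first, c = −50 meets the second. Joined by *and*, the rule is −30 < c < +20. That is what the neither/nor wording of 12.3 gives.

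**Step 3. The reference sum.** Section 6.2 uses both baseline and last set of scans, which allows two readings. The growth rates and sums below are illustrative assumptions; none comes from the documents.

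*Reading A, comparison with the previous scan.* Growth g per interval over k intervals gives (1 + g)^k − 1 above the smallest sum. The g that just reaches +20% is 1.20^(1/k) − 1:

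- k = 1: 20.0%, so a single interval below the limit cannot reach +20%
- k = 2: 9.54%
- k = 3: 6.27%
- k = 4: 4.66%

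Two intervals at 10%, 15% or 19% give 1.10² − 1 = 21.0%, 1.15² − 1 = 32.2% or 1.19² − 1 = 41.6%. In the series 100, 112, 125 the steps are +12.0% and +11.6%, and the total is 125/100 − 1 = 25.0%.

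*Reading B, comparison with a fixed earlier baseline of 100.* A current sum of 119 passes at +19%. Against an intervening smallest sum of 90, 80 or 71 it is 119/90 − 1 = 32.2%, 119/80 − 1 = 48.8% or 119/71 − 1 = 67.6% higher.

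The two-month requirement does not settle which reading applies. Section 10.0 says imaging is often three-monthly, so one scan-to-scan comparison can satisfy it.

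**Step 4. What Step 3 does and does not show.** The reference in 12.3 is "taking as reference the smallest sum of the longest diameters recorded since the treatment started". In a section on on-study response, this most naturally means the study injections, and on that reading no such sum exists before enrolment. Step 3 therefore shows that the two sections measure growth differently. It does not show that a patient with slow earlier growth meets 12.3 progression at entry.

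**Step 5. Reach.** The decision rule in Section 14.0 counts antibody responses in 10 patients, and safety rests on graded toxicity. Neither takes a lesion measurement as input. Planned enrolment is at most 3 + 10 + 10 = 23, and Section 2.1 says the number entering with evidence of disease is unknown, so the number affected cannot be estimated.

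**The case against.** The strongest defence has four parts.

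*The non-target clause in 6.2 may already cover new lesions.* It bars clear worsening of non-target lesions without the word *existing*, so a new non-target lesion could count as worsening. The overall requirement is stable disease for two months, and Section 8.1 requires CT and bone scan within four weeks of the first injection. This reading is possible, and many investigators would adopt it. But 12.3 separates the two events, and *target* in the new-lesion clause of 6.2 has no purpose if all new lesions are barred. The text needs clarifying either way.

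*The literal reading of* or *is pedantic.* A reader might infer that the size limit excludes nobody. The documents do not support that as the intent: it would empty the 20% figure of meaning, and 12.3 expresses the same idea correctly. What stands is a drafting fault.

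*The smallest-sum comparison is not a contradiction.* A reader might infer that slow growers are already progressing under 12.3. That holds only if the 12.3 reference is carried back to the earlier hormonal therapy, which the documents do not do. This objection stands.

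*The consequences are small.* A reader might infer that a progressing patient would remain on a failing therapy, unobserved, to week 23. The documents say otherwise. Section 13.1 has the primary physician told at once of progression and allows continuation with a change of hormone therapy. Section 12.3 provides for evaluation at week 19 or at the physician's discretion. The Section 10.0 table schedules physical examinations at weeks 1, 7, 13, 19 and 23. Section 12.0 does leave follow-up imaging to standard of care. The objection is right that the impact is limited, but it does not remove the mismatch in Step 1.

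**Conclusion.** Sections 6.2 and 12.3 are inconsistent on new non-target lesions: on its literal wording, 6.2 can admit as stable a patient whose new lesion 12.3 would call progression. The *or* and the unclear reference sum are further looseness in the same criterion, not direct contradictions. The first conclusion assumes only that 6.2 is read as written. The reference-sum point assumes that *last set of scans* can mean either the previous scan or an earlier baseline, and its percentages are illustrations, not estimates.

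The effect is limited to the definition of the enrolled population, the descriptive clinical-response reporting and the exploratory CTC analysis. A reader might go further and infer that the immune-response result is compromised, for instance because a progressing patient starts another treatment and leaves before week 19. The documents give no basis for sizing that route, and nothing in the 6-of-10 rule or the safety rules depends on stable disease. The correction is still worth making, because it concerns a stated eligibility rule and changes who may enter.

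**What to change.** Reconcile Section 6.2 with Section 12.3 so that one definition of stable disease applies:

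1. State whether any new lesion, and not only a new target lesion, bars entry.
2. Join the shrinkage and growth limits with *and*.
3. Name one reference sum, saying which scan or period it comes from, and say whether it is meant to match the smallest-sum reference in 12.3.

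Which lesion rule and which reference to adopt is for the sponsor and investigators to decide; the requirement here is that the sections agree.

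The cost is a wording change to one inclusion criterion. A few patients may become ineligible and accrual may slow slightly. If the chosen reference needs earlier serial measurements, these may not be to hand for patients coming from outside the centre, whom Section 7.0 anticipates, so the text should also say what applies when they are missing. No sample size or error rate changes.

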6.3 Subject Exclusion Criteria

- Pregnant women are ineligible. Premenopausal patients must have a pregnancy test to exclude pregnancy within 2 weeks of starting treatment. Women who may yet bear children and sexually active men must use appropriate contraception during the course of this study. Patients must be counseled not to become pregnant during the study. Patients must also be counseled that injection of sLe^a may have unknown affects on the viability of a future fetus.
- Patients who are nursing
- Patients with other active cancers are ineligible, (excluding basal cell or squamous carcinomas of the skin).
- Patients with:
 - total lymphocyte count of $< 0.5 \times 10^6/\text{ml}$.
 - total white blood cell count of $< 3,000 \text{ cells}/\text{cmm}$
 - serum creatinine $> 1.5 \times \text{upper limit of normal}$
 - serum aspartate aminotransferase $> 1.5 \times \text{upper limit of normal}$
 - serum alkaline phosphatase $> 1.5 \times \text{upper limit of normal}$.
- Patients with a history of a seafood allergy.
- Patients with clinically significant NY Heart Association Class 3 or 4 cardiac disease.
- Patients who have previously been immunized with the sLe^a antigen.
- Patients with a known history of immunodeficiency or autoimmune disease. Current use of immunosuppressive medications (ie corticosteroids) is prohibited.
- Active infection requiring antibiotic treatment.

7.0 RECRUITMENT PLAN

Potential research subjects will be identified by a member of the patient's treatment team, the protocol investigator, or research team at Memorial Sloan-Kettering Cancer Center (MSKCC). If the investigator is a member of the treatment team, s/he will screen their patient's medical records for suitable research study participants and discuss the study and their potential for enrolling in the research study. Potential subjects contacted by their treating physician will be referred to the investigator/research staff of the study.

The principal investigator may also screen the medical records of patients with whom they do not have a treatment relationship for the limited purpose of identifying patients who would be eligible to enroll in the study and to record appropriate contact information in order to approach these patients regarding the possibility of enrolling in the study.

During the initial conversation between the investigator/research staff and the patient, the patient may be asked to provide certain health information that is necessary to the recruitment and

enrollment process. The investigator/research staff may also review portions of their medical records at MSKCC in order to further assess eligibility. They will use the information provided by the patient and/or medical record to confirm that the patient is eligible and to contact the patient regarding study enrollment. If the patient turns out to be ineligible for the research study, the research staff will destroy all information collected on the patient during the initial conversation and medical records review, except for any information that must be maintained for screening log purposes.

In most cases, the initial contact with the prospective subject will be conducted either by the treatment team, investigator or the research staff working in consultation with the treatment team. The recruitment process outlined presents no more than minimal risk to the privacy of the patients who are screened and minimal PHI will be maintained as part of a screening log. For these reasons, we seek a (partial) limited waiver of authorization for the purposes of (1) reviewing medical records to identify potential research subjects and obtain information relevant to the enrollment process; (2) conversing with patients regarding possible enrollment; (3) handling of PHI contained within those records and provided by the potential subjects; and (4) maintaining information in a screening log of patients approached (if applicable).

Patients will be recruited for this protocol primarily by their doctor at MSKCC. In addition, patients outside of MSKCC may be aware of this trial from other patients, their local doctors or the National Cancer Information Center.

Once a patient has indicated an interest in participation, he/she will be referred to one of the consenting physicians for further evaluation and discussion of informed consent. If the patient is determined to be eligible, he/she will be registered according to standard MSKCC policy.

Most patients with breast cancer are female, but male patients will not be excluded. Children are excluded from participation in this study since breast cancer is rare in this patient population and therefore toxicity analysis would be of questionable significance.

8.1 PRETREATMENT EVALUATION

Within 2 weeks of the first injection:

Pregnancy test for premenopausal patients

Within 3 weeks of the first injection:

- Complete history and physical examination
- Complete blood cell count with differential and platelet count (CBC)
- Comprehensive panel (COMP): aspartate aminotransferase (AST), alanine aminotransferase (ALT), albumin, alkaline phosphatase, bilirubin, calcium, creatinine, glucose, total protein, BUN, sodium, potassium, chloride, C02
- CEA, CA153(or BR27-29 or CA27-29)

- Thyroid stimulating hormone (TSH) level
- Urinalysis
- Rectal examination with Hemoccult
- Blood (3 red-top tubes) for immune response studies will be sent to [name] laboratory in [name]. An additional 7.5 ml of blood will be drawn in special tubes to go to [name] lab in Clinical Chemistry for assessment of circulating tumor cells. These blood samples may be drawn on the day of the first injection, but prior to the injection.

Within 4 weeks of the first injection:

Imaging and Diagnostic Studies

- CT scan of the chest/abdomen/pelvis
- Radionuclide bone scan

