3.5 Evaluation of Circulating Tumor Cells (CTC)

Circulating tumor cells (CTC) can be detected in the blood from patients with various primary or metastatic carcinomas.²⁵⁻²⁹ Recently the development of immunomagnetic separation strategies has increased the sensitivity of these assays.^{28,29} Several studies have reported that the presence of CTC predicted shortened disease free and overall survival times. These studies demonstrate that detection of CTC correlates with prognosis at baseline and that changes in CTC levels during and after treatment may be more predictive than other measures.³⁰⁻³⁴ Monoclonal antibody based therapy (trastuzumab) with or without additional chemotherapy was particularly effective at eliminating CTC. This was associated with improved disease free and overall survival.²⁸

Use of peripheral blood immunomagnetically enriched for tumor cells using labeled antibodies targeting epithelial cell surface markers on breast cancer cells and quantitated using a CellSpotterAnalyzer is now FDA approved for this purpose in breast cancer patients. Veridex, LLC. has provided MSKCC with a CellSpotterAnalyzer for this purpose in patients with prostate and breast cancer. To date, [name], Chief of the MSKCC Department of Clinical Laboratories, has validated the assay in prostate cancer patient using the same labeled antibodies which are FDA approved for use in breast cancer patients.

Two studies have identified CTC in approximately 95% of breast cancer patients with Stage I/II disease prior to surgery.^{35,26} After resection of all known disease, 30% of patients continued to have CTC that persisted for at least 2 weeks. The patients that we propose to evaluate are patients at a high risk for recurrence. We estimate that at least 30% of these patients will have demonstrable CTC.

In this study, CTC will be evaluated in an exploratory manner to determine whether they can be detected in this patient population at baseline and if so whether there is evidence

of a decline in those patients who have an immune response. CTC will be monitored prior to, during and after injection with sLe^a-KLH plus QS-21. The patient and their primary oncologist will be notified of all CTC results. These results will be used for research purposes and will not be used during the study to alter clinical care. Although some physicians at other centers may use CTC results to evaluate response to therapy, this is not considered standard care at MSKCC.

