14.0 BIOSTATISTICS

This is a pilot study designed to assess the safety and immunogenicity of immunization with sLe^a-KLH plus QS-21 in patients with high risk breast cancer. If immune responses are observed at the 100 mcg level of QS-21 then QS-21 will be escalated to the 150mcg level.

The immunization schedule comprises five injections administered during weeks 1,2,3,7 and 19. The primary endpoint of this trial is to evaluate immunological response to this single antigen and evaluate toxicity. Immunological response for a patient is defined as an antibody response of greater than 1:80 if baseline value was 0 and at least an increase of 8-fold if baseline value is greater than 0. Initially, three patients will be accrued to the study at a dose of 10 mcg of sLe^a. If safe, then ten patients will be accrued to the study at the full 30mcg sLe^a dose. If 6 or more of these 10 patients have an immune response at any time point then an additional 10 patients may be accrued and receive sLe^a-KLH plus QS-21 (at 150mcg) during weeks 1, 7 and 19. This sample size is chosen to minimize the total number of patients who need to be immunized to identify a promising agent with a probability of an immunological response greater than 50% in a series of immunization trials. The error rates of missing a promising agent or selecting a nonpromising agent are set to be at most 10%.³⁶

At the end of the trial a qualitative assessment of the number of responses and frequency of toxicities will be made to determine which dose of QS-21 will be carried forward in future studies.

Severe toxicities are not anticipated. Toxicities will be tabulated according to the NCI CTC version 3.0. Any grade 3 or greater toxicity (excluding grade 3 lymphopenia) or grade 2 or greater allergic/immunologic toxicity (except isolated fever and/or flushing) will result in removal of the patient from the study. Since the above listed toxicities are unexpected, any event of this sort will result in suspension of the study pending further investigation. Descriptive statistics summarizing the antibody responses will be provided for each patient. The length of the study will be approximately 1-2 years.

Circulating tumor cells (CTC) will be evaluated in an exploratory manner to determine whether CTC can be detected in this patient population at baseline and if so whether there is evidence of a decline in those patients who have an immune response.

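### The only pre-vaccine CTC tube may be drawn 3 weeks before injection 1, so the 4-week washout guarantees just 7 days between prior therapy and the CTC baseline

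*Combined protocol and SAP*

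**What the plan says.** Three parts of the protocol bear on the timing of the CTC baseline.

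- **Washout (Section 6.2).** "Patients must have completed radiation, chemotherapy or surgery at least 4 weeks prior to treatment". For immunotherapy, "Patients must have completed prior immunotherapy at least 6 weeks prior to vaccination". Both periods end at treatment; neither refers to a blood draw.
- **Baseline draw (Section 8.1).** Under the heading "Within 3 weeks of the first injection", after the serum tubes for immune response, the list adds: "An additional 7.5 ml of blood will be drawn in special tubes". It continues: "These blood samples may be drawn on the day of the first injection, but prior to the injection". That is a permission. It sets the latest time for the draw and does not require that time.
- **Use of the baseline (Section 14.0).** CTC are exploratory. The question is "whether CTC can be detected in this patient population at baseline and if so whether there is evidence of a decline" in patients with an immune response. Section 2.1 makes CTC monitoring the secondary objective.

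The evaluation table in Section 10.0 marks a CTC assay before the study and next at week 5, with none at week 1. Section 4.2 gives the same first two times. The two places differ on later weeks, which does not matter here.

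**The concern.** The washout protects the first injection, but the CTC analysis depends on the baseline tube, and the two can be 3 weeks apart. If a patient had surgery, radiation or chemotherapy shortly before entry, the tube may record CTC status soon after that therapy. Any later movement as its effect fades would then fall between baseline and the first CTC draw on study.

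Nothing in the design separates that movement from a vaccine effect. Every patient is vaccinated, no adjustment for time since therapy is planned, and no comparison of responders with non-responders is specified. The planned reading is simply "if so whether there is evidence of a decline in those patients who have an immune response". A baseline raised by recent therapy could produce an apparent decline, and one lowered by it could hide a real decline.

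Section 3.5 gives reason to think that CTC status changes around therapy. It reports CTC in about 95% of Stage I/II patients before surgery, and then: "After resection of all known disease, 30% of patients continued to have CTC that persisted for at least 2 weeks".

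**Working it through.** The documents give no sample size, error rate or effect size for CTC, so there is no stated figure to reproduce. The check is interval arithmetic.

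**Inputs**
- Minimum time from surgery, radiation or chemotherapy to injection 1: 4 weeks = 28 days (Section 6.2, taking treatment to mean the first injection).
- Minimum time from immunotherapy to injection 1: 6 weeks = 42 days (Section 6.2).
- Earliest baseline CTC draw: 3 weeks = 21 days before injection 1 (Section 8.1).
- Latest baseline CTC draw: the day of injection 1, lead time 0 (Section 8.1).

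**Formula.** Guaranteed gap from prior therapy to CTC baseline = washout - lead time of the draw.

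| Draw, days before injection 1 | Gap after surgery, radiation or chemotherapy | Gap after immunotherapy |
|---|---|---|
| 21 | 28 - 21 = 7 days | 42 - 21 = 21 days |
| 14 | 28 - 14 = 14 days | 42 - 14 = 28 days |
| 7 | 28 - 7 = 21 days | 42 - 7 = 35 days |
| 0 | 28 - 0 = 28 days | 42 - 0 = 42 days |

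**Interval to the first CTC draw on study.** Week 5 is about 5 - 1 = 4 weeks after injection 1. With the earliest permitted baseline the comparison spans about 4 + 3 = 7 weeks, of which 3 precede any vaccine. With an injection-day baseline it spans about 4 weeks, all of them after vaccination.

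**Does another provision close the gap?**
- No section sets a minimum interval between prior therapy and the CTC tube.
- There is no second pre-vaccine CTC draw.
- Patients entering with stable disease must have been stable on hormonal therapy for at least 2 months before enrollment. That makes recent chemotherapy unlikely, though it does not expressly bar local radiation or surgery.
- Patients entering with no evidence of disease have no such period, only the washout.

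**Scale of the CTC analysis.** Section 3.5 estimates that at least 30% will have detectable CTC. At exactly 30% that is 0.30 x 10 = 3 patients in a group of 10, and 0.30 x 23 = 6.9 if all 23 are enrolled. The analysis is small, but this does not say how many baselines would be affected, because the documents do not state how many entrants will have had recent therapy.

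**The case against.** The strongest reply is that this is a narrow worst case in an exploratory analysis. It needs therapy ending close to day -28 and a tube drawn close to day -21. Injection-day sampling is already allowed and may be common in practice. CTC results have no test or threshold and do not alter care. A single-arm decline could not establish a vaccine effect even with a perfect baseline: ongoing hormone therapy is allowed without washout, and Section 13.1 allows a change of hormone therapy on study after progression. All of this stands and limits the weight of the point. It does not close the gap, and it does not justify leaving the timing of the one reference sample open when fixing it is so easy.

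A reader might also infer stronger things that the documents do not support.

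- **That Section 3.5 shows CTC still clearing at one week, or gives the size of the bias.** It gives one figure before surgery and one for persistence of at least 2 weeks. It has no day-7 value and no clearance curve, and the 30% are described as persisting, not falling. The patients had Stage I/II disease, whereas this trial enrols Stage IV. The earliest permitted baseline is already 7 days after surgery, so the fall from the pre-surgical figure does not measure what could happen after that baseline. For chemotherapy and radiation no figure is given.
- **That the antibody baseline has the same problem.** It does not. Sections 10.0 (table footnote e) and 10.2 require serum before the vaccine at week 1, so an early serum tube is backed up. The CTC tube is not.
- **That a given share of the CTC analysis is compromised.** This would need a responder rate and a count of recently treated entrants. The 6-of-10 figure is a threshold for opening the second group, not an expected rate, and the count is not stated.

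**Conclusion.** The point holds for the CTC tube only. As written, the protocol guarantees 7 days between surgery, radiation or chemotherapy and the CTC baseline, although the 4-week washout might suggest 28. A therapy-related change could therefore enter the uncontrolled comparison with baseline and be read as a change under the vaccine. The exposure is mainly in patients with no evidence of disease.

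Seven days is the permitted minimum, not the expected gap. The conclusion assumes that some patients enter soon after such therapy and that the therapy affects CTC counts; the documents make the second plausible for surgery but quantify neither for this population. The size and direction of any bias cannot be computed from them. Safety, antibody response, the 6-of-10 rule and the choice of QS-21 dose do not depend on CTC and are unaffected. This is a minor weakness with a practically free improvement.

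**What to change.** In Section 8.1, take the CTC tube out of the 3-week window. State that it will be drawn on the day of injection 1, before the vaccine is given, together with the week-1 serology, and define that sample as the CTC baseline. Adjust the pre-study CTC entries in Section 4.2 and the Section 10.0 table to match. In Section 14.0, add that time since last surgery, radiation or chemotherapy will be reported beside each patient's CTC results.

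The guaranteed gap rises from 7 to 28 days (from 21 to 42 for immunotherapy), and the baseline sits immediately before exposure. Carry-over is reduced, not excluded, because the documents do not show that 28 days is free of after-effects; reporting time since therapy lets a reader judge what remains.

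The cost is a few lines of text. Blood is already drawn before the vaccine that day, so no visit or needle stick is added. CTC are not an eligibility criterion, so the result is not needed earlier. The therapy dates have to be known anyway to confirm the washout. No treatment, dose or eligibility rule changes.
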